5.7 Adherence/Compliance

- 5.7.1 Ideally, participants will receive 52 ± 1 weeks of treatment. The required compliance rate for evaluability is $\geq 80\%$. Doses that are missed due to drug holidays (as described in Section 5.6) will not count as non-compliance.
- 5.7.2 The participant's compliance will be measured by evaluating study calendars and pill counts. Participants will be informed, both verbally and in writing at all visits of the following important compliance points:
- Bring all bottles of study drug (whether or not there is medication in the bottle) to study visits.
 - Bring completed pill diary to study visits.

6. PHARMACEUTICAL INFORMATION

6.1 Study Agent (IND #, IND Sponsor)

POMx™ is a pomegranate (*Punica granatum* L., Wonderful variety) fruit polyphenol extract, which was developed for use as a dietary ingredient. Each capsule contains up to 1000mg of PFE, which delivers pomegranate polyphenols in an amount equivalent to about 8 oz of pomegranate juice. POMx™ powder is produced in a two-step process: (1) extraction of polyphenols from pomegranate fruit, and (2) purification of the extract to produce a highly concentrated polyphenol powder. Extraction is performed during the fruit harvest using pressed pomegranate skins and arils with the seed completely removed. Purification of the extract is performed off-season to meet market demand. Appropriate product specifications have been established, and batch analyses data confirm the product is consistent in quality and free of microbial or chemical contaminants.

The extract is well characterized. It contains the same compounds found in pomegranate juice, and differs only in having lower anthocyanidins, significantly higher proportional content of pomegranate polyphenols, primarily punicalagin and isomers, but the levels in food or supplement products are limited to the amount found in 8 oz of 100% juice. Although punicalagin is unique to pomegranate, its metabolism is known to be like that of other polyphenols. The metabolism of pomegranate polyphenols is reasonably well understood in mice, rats, and humans. Like most dietary polyphenols, pomegranate polyphenols are hydrolyzed in the gut and also metabolized by gut microflora.

POMx™ is a premium grade of pomegranate ellagitannins produced from pomegranate fruits. The extract is from pomegranate skins and arils minus the seeds. POMx™ is standardized to 37% punicalagins, the major pomegranate ellagitannin, and 3.5 % ellagic acid (Seeram et al., 2005; Sartippour et al., 2008). POMx™ is standardized to 60% Gallic Acid Equivalents (GAE) and 85% Total Pomegranate Polyphenols (TPP). POMx™ will be provided by POM Wonderful (Los Angeles, CA, USA).

The investigation product is composed of 1050mg (*Target Fill Weight*) of hygroscopic POM Wonderful pomegranate extract (PWPE) powder blended with 10mg of magnesium stearate (lubricant) and 10mg silicon dioxide (glidant) contained in a size "0" gelatin capsule.

Ingestion of POMx™ results in a level of intake that remains within safe limits established by the history of safe consumption of pomegranate fruit and juice, and is corroborated by published human and animal studies. POMx™ has been sufficiently characterized to assure that it is a safe and wholesome food.

6.2 Reported Adverse Events and Potential Risks

In 21 clinical studies involving 898 human subjects, POMx™ has been very well tolerated. The most commonly reported adverse events have been gastrointestinal effects reported by less than 2% of people taking 1000 mg of POMx™, increasing to

12% at 3,000 mg. Paller et al (2012) in a trial comparing 1000 to 3000 mg of POMx™ over 18 months of intervention reported 12 gastrointestinal events (101 participants, median age 72). These events included diarrhea (1.9% in the 1000 mg group, 13.5% in the 3000 mg group – five of these events at this dose level were deemed drug-related); reflux disease (1 participant in the 1000 mg group); nausea (4 participants at 3000 mg); and abdominal pain, constipation, frequent bowel movements, stomach discomfort, and vomiting (1 participant each at 3000 mg). This study also reported several cardiac events including angina pectoris, arrhythmia and congestive heart failure. Three occurred in the 1000 mg group and seven in the 3000 mg group. Most of these events occurred in participants who were diagnosed with cardiac conditions prior to randomization and none of these events were considered to be drug related. The study did not include a placebo control group. There are no other reports in the literature of cardiac events associated with POMx™.

6.3 Availability

POM Wonderful will provide POMx™ to NCI, DCP in sufficient quantities to complete the study. POMx™ will be dispensed to the POs by the DCP repository contractor MRIGlobal.

6.4 Agent Distribution

Agents will only be released by NCI, DCP after documentation of IRB approval of the DCP-approved protocol and consent is provided to DCP and the collection of all Essential Documents is complete (see DCP website for description of Essential Documents).

DCP does not automatically ship study agent; the University of Wisconsin must make a request for agent to be shipped to the PO on a per-participant basis. University of Wisconsin staff will complete the DCP Clinical Drug Request form (NIH-986, to include complete shipping contact information) and fax the form to the DCP agent repository contractor:

NCI-DCP Repository
MRIGlobal
Attn: [name]
[name]
[name]
[contact]
[contact]
Email: [contact]

DCP does not permit the transfer of agents between institutions (unless prior approval from DCP is obtained).

6.5 Agent Accountability

The Investigator, or a responsible party designated by the Investigator, must maintain a careful record of the inventory and disposition of all agents received from DCP using the NCI "Investigational Agent Accountability Record". The Investigator is required to maintain adequate records of receipt, dispensing and final disposition of study agent. Include on receipt record from whom the agent was received and to whom study agent was shipped, date, quantity and batch or lot number. On dispensing record, note quantities and dates study agent was dispensed to and returned by each participant.

6.6 Packaging and Labels

Study drug (1,000mg PFE/capsule or placebo) will be packaged in standard 100 CC white, pharmaceutical-grade, sealed bottles containing 30 capsules each. DCP will affix a label on each of the bottles; the randomization code will be printed on the label.

6.7 Storage

Investigational product should be stored in dry conditions at room temperature.

6.8 Registration/Randomization

Subjects who are eligible must be randomized by faxing randomization materials to the University of Wisconsin CLO. The PO's study coordinator will complete the Baseline Visit Guide and the Eligibility Questionnaire and [contact]) or e-mail ([contact]) both along with a de-identified copy of the participants Informed Consent form, the clinical lab report and the pathology report from the pre-study baseline prostate biopsy to the CLO central randomization desk. The CLO coordinator at the randomization desk will review eligibility, confirm that the correct consent form version is being used and assign a randomization number.

The CLO will then fax a Clinical Drug Request form to the DCP Drug Repository requesting that drug be shipped overnight to the PO. The Drug Repository will not randomize participants but will maintain a randomization list with treatment assignment codes so they can dispense the correct study product. For next day delivery, the CLO must receive a request for randomization by 12:00 CST on the business day before the drug is needed. Study agent cannot be shipped on a Friday or the day before a holiday. There may be instances where a five-day turn-around is needed (holidays or unusual circumstances). If possible, please randomize a week before the study agent is needed.

As soon as a subject has been randomized, the CLO will email a confirmation of randomization to the PO's study coordinator. If POs do not receive a confirmation within two hours, they should call the CLO to confirm that randomization documents were received. Drug will then be shipped to the PO via overnight courier.

6.9 Blinding and Unblinding Methods

This will be a double-blind study. Neither the participant nor the study personnel will know which treatment arm a participant is on. The Biostatistical Office of the Chemoprevention Program under the guidance of [name] will have the randomization code to unblind subjects. Unblinding of subjects will not occur until the study has been completed by all participants and all data has been collected and analyzed. If a participant experiences a healthcare-related event and unblinding is requested to facilitate their care, the treating physician will contact Drs. [name] and/or [name] with the request to unblind. The request to unblind will be approved upon the agreement of the NCI medical monitor for this protocol. Unblinded participants will be removed from further study participation.

If the request to unblind is approved, the PO will be directed to the product tear-off label which is removed from the study agent bottles at the time they are dispensed and placed in the participant's study chart or other designated research record. The label has a scratch off area that will disclose the treatment assignment.

The PO will immediately notify the CLO of the unblinding by e-mail ([contact]) and will document the unblinding process in the participant's study chart.

The Medical Monitor must be notified that the blind has been broken.

[name]
Chief, Prostate and Urologic Cancer Research Group
Division of Cancer Prevention, National Cancer Institute, NIH, DHHS
Shady Grove Campus
[name]
[name]
[contact]
[contact]

6.10 Agent Destruction/Disposal

At the completion of investigation, all unused study agent will be returned to the NCI, DCP Repository according to the DCP "Guidelines for AGENT RETURNS" and using the DCP form "Return Drug List".

7. CLINICAL EVALUATIONS AND PROCEDURES

7.1 Schedule of Events

Evaluation/Procedure	Baseline	Randomization	Week 13 (+/- 1 week) ¹	Week 26 (+/- 1 week) ¹	Week 39 (+/- 1 week) ¹	Week 52 ± 1 Week (or end of study therapy) ¹
Informed consent	x					
Registration	x					
Eligibility Criteria Review	x					
Medical History	x					
Physical Exam	x			x		x
Vital Signs (Temp, BP, Pulse, Respirations) and Weight	x		x	x	x	x
Height	x					
ECOG Performance Status	x					
Assess baseline symptoms	x					
Eligibility/Safety Labs ²	x		x	x	x	x
Total PSA ³	x		x	x	x	x
Randomization		x				
Dispense study medication and diary		x ⁴	x	x	x	
Pill count and drug calendar review			x	x	x	x
Review concomitant medications	x		x	x	x	x
Assess adverse events						x
Prostate Biopsy	x ⁵					x ⁶
The samples listed below will be collected locally, and shipped to UWI for analysis:						
Collect one 3ml red top ⁷	x		x	x	x	x
Collect a second 3ml red top ⁷	x			x		x
Two 10ml green tops ⁷	x		x	x	x	x
Urine collection ⁷	x		x	x	x	x
IHC analysis of normal and abnormal prostate tissue biomarkers (PSA, IGF-1, IGFBP-3, apoptosis [CASPASE 3], Ki-67, IGF-IR, 8OHdG and androgen receptor)	x ⁸					x ⁹

¹The participant must delay his dose of study medication until after blood and urine has been collected, as PK levels need to be assessed approximately 24 hours following the last dose of study medication.

²The following lab tests are to be performed: WBC, Hemoglobin, Platelets, Alkaline Phosphatase, ALT, AST, Total Bilirubin, Serum Creatinine, Sodium, Potassium, Chloride, and Bicarbonate. Eligibility labs must be done \leq 30 days of randomization.

³This total serum PSA will be performed at the PO's clinical lab, and used for clinical purposes.

⁴If the participant is unwilling or unable to return to clinic to pick up study medication, it may be sent overnight by a courier service such as UPS or Fed-Ex.

⁵ The baseline biopsy must have occurred within 13 months prior to the baseline study visit.

⁶The end of study biopsy performed during week 52 ± 1 week or when participant discontinues study therapy. Participant must take study drug the morning of the biopsy after research blood and urine collection but prior to the biopsy.

⁷These blood and urine samples will be used to determine study objectives (PK and biomarker results) as described in §1.2. See §10.2 for collection and processing instructions.

⁸Tissue will be from a biopsy performed within 13 months of study entry

⁹Tissue will be from the end of study biopsy (or prostatectomy, if applicable)

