- **Week 26 Visit:** Physician visit, safety labs and total PSA (to be processed at the PO's clinical lab), review of adverse events and concomitant medications, pill count and compliance review, blood and urine collection for research purposes (batch shipped to the CP lab at UWI for analysis of total serum PSA, plasma pharmacokinetics and biomarkers and urine pharmacokinetics).

- **Week 52 ± 1W or End-of-study visit:** Physician visit, safety labs and total PSA (to be processed at the PO's clinical lab), review of adverse events and concomitant medications, pill count and compliance review, blood and urine collection for research purposes (batch shipped to the CP lab at UWI for analysis of total serum PSA, plasma pharmacokinetics and biomarkers and urine pharmacokinetics).
 - Prostate Biopsy – participants will undergo a “standard-of-care” prostate biopsy (8-12 cores from apex, mid-gland, base). Should a study participant elect to undergo surgery, prior to completion of the 12 month study period, (secondary to progression or participant preference) efforts will be made to obtain prostate tissue from the prostatectomy for histology and molecular studies (PSA, IGF-1, IGFBP-3, apoptosis (CASPASE 3), Ki-67, IGF-1R, 8OHdG and androgen receptor), and to obtain all other end of study assessments.
 - If the participant discontinues study therapy and a prostatectomy is not planned, if at all possible, perform a biopsy prior to the participant initiating non-study therapy and obtain all other end of study assessments.
 - Plasma and urine ellagic acid, dimethyl ellagic acid, urolithin A, urolithin B and their corresponding glucuronides will be evaluated by LCMSMS as previously described by Seeram (Seeram et al, 2006). LCMSMS is a standard analytical technique with improved sensitivity over HPLC.

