5.6 Dose Modification

The study drug dose modification schema is as follows:

IF	THEN
The participant experiences a grade 2 adverse event that is possibly, probably, or definitely related to study drug	Stop study drug temporarily for up to 4 weeks.
The adverse event resolves to \leq grade 1 within 4 weeks:	Re-start study drug at 50% dose reduction (1 capsule should be administered every other day).
If the adverse event does not resolve to \leq grade 1 within 4 weeks:	Stop study drug permanently. Continue to follow participant per the schedule of events in Section 7.1, if participant is willing.
If the participant experiences a grade 2 event after initial dose reduction, and the adverse event is possibly, probably or definitely related to study drug:	Stop study drug permanently and follow until the adverse event is resolved to \leq grade 1. Continue to follow participant per the schedule of events in Section 7.1, if participant is willing.
In the event a subject had study drug stopped while on the 50% dose reduction, for a grade 2 adverse event that is NOT possibly, probably or definitely related to study drug	Stop study drug temporarily for up to 4 weeks. If the adverse event resolves to \leq grade 1 within 4 weeks, re-start study therapy at the 50% dose reduction level. If the adverse event does NOT resolve to \leq grade 1 within 4 weeks, permanently discontinue study drug. Continue to follow participant per the schedule of events in Section 7.1, if participant is willing.
A grade 3 or 4 adverse event occurs, regardless of relationship to study drug	Stop study drug and call protocol chair to determine if and when drug should be re-started.

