7.3.2.2 Collection of Blood and Urine for Research Purposes

In addition to the blood drawn for clinical safety labs, two 3ml red top tubes and two 10ml green top tubes of blood will be collected for research assays using the supplies provided in the research lab kit. A minimum of 10ml of urine will be collected in a urine collection cup. The cup is not provided in the research lab kit. Instructions for collection, handling and shipping of research blood and urine samples are in sections 10.2 and 10.3 of this protocol.

7.4 Evaluations at Completion of Study Intervention (Week 52±1W or end of study therapy)

The Week 52 Visit (or end-of-study therapy visit, whichever comes first) is identical to the week 13 and 39 visits as described in section 7.3.1 with the following additional evaluations:

- a physical exam
- collection of a second 3ml red top tube for research biomarker assessment
- a prostate biopsy

As for the previous visits, the participant will be instructed to delay his dose of study agent on the day of this visit until AFTER blood and urine samples have been collected to allow for a 24-hour post dose pharmacokinetic assessment. **However, the participant WILL be instructed to take his final dose of study agent immediately following the collection of the research blood and urine samples and prior to the prostate biopsy to allow for the assessment of study agent levels in prostate tissue.**

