7.4.2. Prostate Biopsy

NOTE THAT THE STANDARD- OF-CARE PROSTATE BIOPSY MUST BE PERFORMED DURING STUDY WEEK 52±1W, OR AT THE TIME THE PARTICIPANT DISCONTINUES STUDY THERAPY. If the participant discontinues study therapy to undergo a prostatectomy, tissue samples can be obtained at the time of prostatectomy.

If the participant discontinues study therapy and a prostatectomy is not planned, if at all possible, perform a biopsy prior to the participant initiating non-study therapy.

Prostate biopsies (≥ 8 core samples from all quadrants of the prostate) will be performed at end of study or at the time of study withdrawal and submitted for standard of care histopathologic grading at the participating organization.

If a study participant elects to undergo prostatectomy prior to completion of the 1-year study period (whether or not they have clinical evidence of disease progression) every effort will be made to obtain prostate tissue from the prostatectomy specimen for histology and molecular studies as described above. Data from prostatectomy samples will be viewed as exploratory.

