The POs will request formalin-fixed, paraffin-embedded tissue blocks from the pre-study baseline and end of study prostate biopsies for submission to the 3P Lab. The CLO will review each participant’s pre- and post-intervention pathology report and select the blocks to be submitted for analysis. This will include location matched blocks of entirely benign cores of prostate tissue, location matched blocks with tumor cores and any additional blocks with tumor cores.

Tissue blocks will be returned to the POs pathology department upon request.

If the pathology department holding the biopsy tissue will not release tissue blocks, 10 unstained slides may be substituted. The slides should be cut in 4-5 um-thick sections and picked up on Super Frost Plus or comparably charged slides. These slides should not be pre-melted or baked. If there is insufficient tissue in the block to cut 10 sections, the remaining sections may be cut from another block containing adenocarcinoma (if another block is available from the same biopsy is available).

If the POs pathology department’s policy is not to release blocks immediately after biopsy, the request for blocks may be delayed up to 2 months in order to provide adequate time for pathological processing of the blocks.

Procedure notes and pathology reports: Once the procedure notes and pathology reports are available, blinded copies should be added to the participant’s chart. Additionally, copies should be forwarded to the central lab with the shipment of the participant’s research kit.)

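### The mandatory biopsy-morning dose is not reconciled with the Section 5.6 stopping rules, and its stated tissue-level purpose matches no planned measurement

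*Combined protocol and SAP*

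**What the plan says.** **The biopsy-morning dose.** Footnote 6 in Section 7.1 covers a biopsy at week 52 ± 1 week and one done when the participant comes off study therapy. Its second sentence reads: "Participant must take study drug the morning of the biopsy after research blood and urine collection but prior to the biopsy". Section 7.4 gives the same instruction for the week 52 or end-of-therapy visit, whichever is earlier, and supplies the reason: the dose is taken "prior to the prostate biopsy to allow for the assessment of study agent levels in prostate tissue". Section 7.4.2 confirms that the biopsy may fall at week 52 "OR AT THE TIME THE PARTICIPANT DISCONTINUES STUDY THERAPY".

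**The stopping rules.** Section 5.6 has these rows:
- A related grade 2 event not resolved within 4 weeks: "Stop study drug permanently. Continue to follow participant per the schedule of events in Section 7.1, if participant is willing".
- A second related grade 2 event after dose reduction: "Stop study drug permanently and follow until the adverse event is resolved" to grade 1 or less, again with continued follow-up on the 7.1 schedule.
- A grade 3 or 4 event of any cause: "Stop study drug and call protocol chair to determine if and when drug should be re-started".

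Section 8.3 adds further reasons for coming off agent, including adverse events and medical contraindication.

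**What is measured.** On the constituents of the extract, Section 3 says: "Plasma and urine ellagic acid, dimethyl ellagic acid, urolithin A, urolithin B and their corresponding glucuronides will be evaluated by LCMSMS". For tissue, Section 10.2 has sites request "formalin-fixed, paraffin-embedded tissue blocks from the pre-study baseline and end of study prostate biopsies", with unstained slides as a substitute.

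**The concern.** Two things do not fit together. First, a man whose drug has been stopped for an adverse event stays on a schedule whose biopsy footnote makes a dose mandatory and expressly includes biopsies at discontinuation. A site reading both sections literally is told to stop the drug and to have it taken. At stake is re-exposure of a man already stopped for safety, or inconsistent handling between sites.

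Second, the dose is justified only by a measurement that appears nowhere else in the plan. A mandatory instruction with a safety consequence should have a purpose that the trial is set up to serve.

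**Working it through.** The plan gives no figure on this point, so the check sets the sections side by side. A short calculation on size follows.

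**Step 1: does footnote 6 reach men whose drug has been stopped?**
- Trigger in footnote 6: week 52, or discontinuation of therapy. Sections 7.4 and 7.4.2 agree.
- Instruction attached to that trigger: mandatory dose, no exception stated.
- Section 5.6, permanent stop for a related grade 2 event: follow-up continues on the 7.1 schedule, if the man is willing. Whether his biopsy is done at discontinuation or at week 52, footnote 6 is the text that governs it.
- Section 5.6, grade 3 or 4: restart is reserved to the protocol chair. Footnote 6 makes no reference to that decision.
- Section 8.3: a man taken off agent for an adverse event or medical contraindication, and then biopsied as Section 7.4.2 asks, meets the same footnote.
- Searching the rest of the protocol for an exemption finds none.

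**Step 2: who is outside the conflict?** A man who completes 52 weeks, or who chooses to stop, can take the biopsy-morning capsule as his last one. No stopping rule forbids it. The conflict is therefore confined to stops under Section 5.6 and safety stops under Section 8.3.

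**Step 3: does anything in the plan measure agent in tissue?**
- Objectives: 1.2.5 covers plasma and urine trough levels only.
- Endpoints and analysis: 8.2, 13.1 and 13.5 list no tissue level of the agent.
- Assays: Section 3 specifies LC-MS/MS for plasma and urine. Section 10.1 assigns pharmacokinetic work on those two matrices.
- Tissue: fixed blocks or slides (10.2), analysed by immunohistochemistry of protein markers (9.1, 9.2).
- Research blood and urine are drawn before the dose, so they do not capture it either.

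Two mentions could be mistaken for support. Section 7.2 groups tissue with blood and urine when describing destruction of samples from ineligible men, but sets up no tissue assay. The tissue ellagic acid endpoint in Section 2.2.1 belongs to a cited pre-prostatectomy study.

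**Step 4: how many men?** The documents give no rate of permanent stops. Section 6.2 reports gastrointestinal effects in under 2% of people at 1000 mg. Taking 2% as an upper figure and 15 men on extract (Section 13.2):
- Expected number with such an event: 15 × 0.02 = 0.3.
- Chance of at least one: 1 − 0.98^15 = 1 − 0.739 = 0.26.
- Chance of two or more: 1 − 0.98^15 − 15 × 0.02 × 0.98^14 = 1 − 0.739 − 0.226 = 0.035.

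This overstates stops for gastrointestinal reasons, because a permanent stop needs a related grade 2 event that persists or recurs. It leaves out other related events, and grade 3 or 4 events of any cause, whose rates are not given. A working range of 0 to 2 of the 15 men on extract is an assumption.

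**The case against.** The strongest reply is that the conflict needs an over-literal reading. The 7.1 schedule also dispenses medication at weeks 13, 26 and 39, and its footnote 1 assumes a dose about 24 hours before sampling. Nobody would take that as an order to supply drug to stopped men; the natural reading is that assessments continue and dosing items apply to men on agent. Section 7.4 speaks of a delayed daily dose and a final dose, which suggests a man still taking capsules. Section 5.6 is also the more specific rule.

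Much of this stands as a prediction of how most sites would act. It does not remove the gap. Unlike the dispensing row, footnote 6 names discontinuation as one of its two occasions and attaches a mandatory instruction to it. No text says which section prevails.

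Other parts of the reply stand in full, and they rule out several inferences a reader might draw:
- **That the instruction adds an exposure that disturbs the tissue biomarkers.** For men on agent it is the ordinary morning capsule (Sections 5.1 and 5.2), ordered relative to sampling. The one-hour plasma peak for ellagic acid in Section 2.2.2 comes from other studies and shows no effect on tissue markers.
- **That tissue levels could not be obtained from the samples.** The documents do not say fixed tissue is unsuitable for assay, and Sections 10.4 and 14.4 allow for later use of stored material. What they show is that no such measurement is planned.
- **That dose time needs a new data field.** The diary in Section 7.2.12 already records the date and time of each dose.

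**Conclusion.** The point holds in a limited form. Footnote 6 and Section 7.4 conflict with Section 5.6, and with safety stops under Section 8.3, for men whose agent has been stopped on those grounds; no section resolves this. The stated tissue-level purpose has no matching objective, endpoint, assay or analysis.

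The number of men touched is probably very small, on the assumption that related events are about as rare as Section 6.2 suggests. A reader might infer that the problem reaches everyone who discontinues, or all 30 participants because the rule is blinded. It does not: only stops under 5.6 or for safety under 8.3 create a conflict, and a stopped man on placebo would not be re-exposed to extract.

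Nor does it threaten the primary result. Research blood is drawn before the dose, so plasma IGF-1, trough levels and the research PSA are unaffected. This is a correction worth making because it concerns a mandatory instruction with a possible safety consequence, but it falls short of a must-fix. Which clinical rule should prevail is for the sponsor and investigators.

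**What to change.** 1. Reconcile Sections 5.6, 7.1 (footnote 6), 7.4, 7.4.2 and 8.3 so that the biopsy-morning instruction states whether it applies to men whose agent has been stopped, including those awaiting the protocol chair's decision. The sponsor decides the rule.
2. In Section 7.4, either remove the tissue-level purpose, or keep it and add the specimen, the assay and the analysis that would deliver it, with a matching objective.

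The reconciliation and the removal are wording changes: no added participants, samples, procedures or data fields. Keeping the tissue purpose would cost an assay and possibly further specimen handling, which the sponsor would need to specify.
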